9.1.8 Shedding of RV3-BB

Only rotavirus VP6 PCR positive and "RV3 vaccine-like" responses will be summarised for RV3-BB shedding. Positive PCR samples that are sequenced as "wild type-like" by sequence analysis will not be included in RV3-BB shedding but will be listed.

The number and proportion of participants shedding RV3-BB on one of days 3-5 following each dose of investigational product will be summarised for each dose number, by treatment group using frequency tabulations. In addition, the number and proportion of participants shedding according to NSP3 PCR on one of days 3-5 following each dose

of investigational product will be summarised for each dose number, by treatment group using frequency tabulations.

9.1.9 New shedders

(VP6 PCR positive and "RV3 vaccine-like" responses) will be summarised in frequency tabulations for the number and proportion of participants who are "new shedders", at doses 2, 3 and 4.

9.1.10 Diarrhoea endpoint

The presence of rotavirus and the severity of episodes in diarrhoea samples will be summarised (n, %) and listed by treatment group. Description of the occurrence of diarrhoea episodes in participants, according to severity and strain of wild-type rotavirus will be listed.

9.1.11 Other endpoints:

- Comparison of the geometric mean titre of the anti-rotavirus serum IgA response after 3 doses of RV3-BB between the neonatal schedules versus the infant schedule.
- Description of safety and tolerability (as per sections 15 to 16 of this analysis plan) of RV3-BB, for the neonatal schedules versus the infant schedule.

9.1.12 Exploratory endpoints:

 Histo-blood group antigens (HBGA) status of participants in association with antirotavirus sero-conversion and cumulative vaccine take after 3 doses RV3-BB administered in either the neonatal schedule (any titre) or infant schedule. The number and proportion of participants for HBGA status (HBGA phenotype) will be presented overall for treatment group and by dose. HBGA phenotyping is determined by detection of antigens A, B, H, and Lewis a and b in saliva by enzyme-linked immunosorbent assay (ELISA). Infants with detectable salivary A, B, or H antigen are classified as secretors. Where detection of A, B, and H antigens was negative or borderline, secretor status was confirmed by ELISA to detect lectin antigen. Infants who were positive for either Lewis a or Lewis b antigen were classed as Lewis positive, and those negative for both Lewis antigens as Lewis negative. *FUT2* genotype is determined for infants of nonsecretor phenotype (ie ABH negative). FUT2 genotyping results are "non secretor" (se/se) "secretor" (Se/Se or secretor (se/Se).

The HBGA phenotype status will be listed by treatment group on the FAS population.

Vaccine take and components of, shedding and IgA seroconversion will be summarised by HBGA phenotype for the neonatal (any titre) and infant schedules after three doses of RV3-BB.

HBGA Phenotyping criteria:

А, В, Н	Lewis b	Lewis a	Lectin	HBGA Phenotype
At least 1 positive	Positive	Negative	Not required	Secretor Lewis positive
At least 1 positive	Negative	Negative	Not required	Secretor Lewis negative
At least 1 positive	Positive	Positive	Positive/weak positive	Partial secretor Lewis positive
All negative	Positive or negative	Positive	Negative	Non-secretor Lewis positive
All negative	Negative	Negative	Negative	Non-secretor Lewis negative

The number and proportion of ABO blood type will be presented overall by treatment group. ABO typing is deduced in participants that are secretor negative (ie negative to ABH) have been typed using "whole blood typing" to determine ABO blood type as blood type cannot be deduced by the A,B,H ELISA results. "wholebloodtyping" result present the blood type as A, AB, B and 0. For secretor positive the blood type is determined as follows;

Group A	Group B	Group 0(H)	
result	result	result	Blood type
Neg	pos		A

Pos	neg	В
Pos	pos	0
Neg	neg	AB

The ABO blood type will be listed by treatment group on the FAS population.

 To assess maternal anti-rotavirus IgA and IgG levels in association with antirotavirus IgA seroconversion and cumulative vaccine take in participants following receipt of RV3-BB administered in either the neonatal schedule (at any vaccine titre) or infant schedule at a vaccine titre of 1x10⁷.

Maternal Serum IgA and IgG titres will be summarised, by treatment group using geometric means titres and the mean and standard deviation on the log scale. Measurements below the lower limit of detection will be assigned a value of half of the limit of detection for analysis e.g., if IgA or IgG is <20, this will be assigned a value of 10. This will be performed by the laboratory personnel prior to data transfer. The number of participants (and proportion) with measurements below the lower limit of detection will also be presented, using frequency tabulations. Maternal Serum IgA and IgG titres will also be listed on log scale by treatment group on FAS population.

- Participants in the FAS with samples included in the microbiome subset for exploratory analyses will be listed.
- Participants in the FAS with samples included in the immune development subset for exploratory analyses will be listed.

10. Participant disposition and withdrawal

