A baseline stool sample will be collected from pre-consented participants any time prior to the administration of the first dose of IP. A Stool sample will be collected from randomised participants on day 3, 4 or 5 following each dose of IP. Samples will also be collected for any cases of diarrhoea (defined as 3 or more stools within a 24 hour period that are looser than normal for that participant). Up to two samples will be collected during each diarrhoea episode. Stool and diarrhoea samples will be tested at the local study laboratory for excretion of rotavirus using PCR.
Up to approximately 1-2.5 mL venous blood will be collected from randomised participants within the 2 days prior to each IP dose and at 18 weeks.

	Participants will be followed up for the duration of the study, until 18 weeks of age. Face to face visits will be conducted at least monthly. Adverse events, including diarrhoea episodes, will be recorded for the duration of the study.
Entry Criteria	Inclusion criteria:
	 Neonate is less than 6 days (≤144 hours) of age at the time of first dose. Neonate is in good health as determined by clinical judgment, including a medical history and physical exam, which confirms the absence of a current or past disease state considered significant by the investigator. Neonate birth weight 2500-4000g inclusive or 2250-4000g inclusive at Visit 1. Neonate's parents/guardians expect to be available for the duration of the study, and agree to adhere to all protocol requirements. Neonate's parents/guardians have provided written informed consent prior to study-related procedures being performed.
	Exclusion criteria:
	• Any medical, psychiatric, or social condition of a parent/guardian that in the opinion of the investigator would prevent the neonate's parents/guardians from giving proper informed consent or from complying with the study protocol.
	 Neonates with known or suspected major congenital malformations or genetically determined disease. Neonates with intussusception.
	 Neonates with a known or suspected bleeding diathesis, or any condition that may be associated with a prolonged bleeding time. Neonates who have ever received any blood products, including immunoglobulin, or for whom receipt of any blood product during the course of the study is anticipated.

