4.2 Secondary Objectives

The secondary objectives of the study are;

- To assess the cumulative anti-rotavirus serum IgA response (defined as a ≥3 fold increase from baseline) 4 weeks after 3 doses of RV3-BB administered in an infant schedule at a vaccine titre of 1 x 10⁷.
- To assess cumulative vaccine take and components of vaccine take after 3 doses of RV3-BB (titre of 1 x 10⁷) administered in a neonatal schedule versus three doses of RV3-BB in an infant schedule at a vaccine titre of 1 x 10⁷.
- To assess cumulative vaccine take and the components of RV3-BB vaccine take after 3 doses of RV3-BB administered as a neonatal schedule at a vaccine titre of 1 x 10⁷, 3 x 10⁶ or 1 x 10⁶.

To assess cumulative vaccine take and the components of vaccine take after 2 doses of RV3-BB administered as a neonatal schedule at a vaccine titre of 1×10^7 , 3×10^6 or 1×10^6 or 2 doses in the infant schedule at a vaccine titre of 1×10^7 .

- To assess cumulative vaccine take and components of vaccine take after the first dose of RV3-BB administered as a neonatal schedule at a vaccine titre of 1 x 10⁷, 3 x 10⁶ or 1 x 10⁶ compared to placebo (1st dose of IP in the infant schedule).
- To assess cumulative vaccine take and components of vaccine take after the first dose of RV3-BB at a vaccine titre of 1 x 10⁷, 3 x 10⁶ or 1 x 10⁶ in the neonatal schedule compared with the first dose of RV3-BB at a vaccine titre of 1 x 10⁷ in the infant schedule.
- To describe the geometric mean titre of the anti-rotavirus serum IgA response after 3 doses of RV3-BB administered as a neonatal or an infant schedule
- To describe the safety and tolerability of RV3-BB when administered as an infant or as a neonatal schedule.
- To describe the occurrence of diarrhea episodes in participants, according to severity and detection of wild-type rotavirus.

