2.1.2 Secondary objectives

The secondary objectives of this study are:

- To assess the cumulative anti-rotavirus serum IgA response (defined as a ≥3-fold increase from baseline) 4 weeks after 3 doses of RV3-BB administered in an infant schedule at a vaccine titre of 1x10⁷.
- To assess cumulative vaccine take and components of vaccine take after 3 doses of RV3-BB (titre of 1x10⁷) administered in a neonatal schedule versus three doses of RV3-BB in an infant schedule at a vaccine titre of 1x10⁷.
- To assess cumulative vaccine take and the components of RV3-BB vaccine take after 3 doses of RV3-BB administered as a neonatal schedule at a vaccine titre of 1x10⁷, 3x10⁶ or 1x10⁶.
- To assess cumulative vaccine take and components of vaccine take after 2 doses of RV3-BB administered as a neonatal schedule at a vaccine titre of 1x10⁷, 3x10⁶ or 1x10⁶ or 2 doses as an infant schedule at a vaccine titre of 1x10⁷.
- To assess cumulative vaccine take and components of vaccine take after the first dose of RV3-BB administered as a neonatal schedule at a vaccine titre of 1x10⁷, 3x10⁶ or 1x10⁶ compared to placebo (1st dose of IP in the infant schedule).
- To assess cumulative vaccine take and components of vaccine take after the first dose of RV3-BB at a vaccine titre of 1x10⁷, 3x10⁶ or 1x10⁶ in the neonatal schedule compared with the first dose of RV3-BB at a vaccine titre of 1x10⁷ in the infant schedule.
- To describe the geometric mean titre of the anti-rotavirus serum IgA response after 3 doses of RV3-BB administered as a neonatal schedule or an infant schedule.

- To describe the safety and tolerability of RV3-BB when administered as an infant or as a neonatal schedule.
- To describe the occurrence of diarrhoea episodes in participants, according to severity and detection of wild-type rotavirus.

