3.1.1 Immunogenicity endpoints

Immunogenicity will be assessed through:

- Serum anti-rotavirus IgA response (defined as a ≥3 fold increase from baseline) at each serum collection time-point to 4 weeks after 3 doses of RV3-BB.
- Serum anti-rotavirus IgA levels at each serum collection time point.
- Vaccine take defined as at least a threefold increase in serum anti-rotavirus immunoglobulin A (IgA) from baseline to post IP dosing, or detectable RV3 shedding in stools (by ELISA or PCR) any day from day 3 to 5 following administration of IP.
- Cumulative vaccine take defined as vaccine take observed at the current assessment time point or following any previous dose.
- Anti-rotavirus IgA response (defined as at least a threefold increase from baseline to post IP dosing) at each serum collection time point.
- Presence of RV3 shedding in stools (by ELISA or PCR) from day 3 to 5 following each dose of IP.
- Anti-rotavirus IgA titres defined as geometric mean titres at each serum collection time point.
- Episodes of diarrhoea, from the time of randomisation to 28 days following the last dose of IP. Episodes will be confirmed by Rotavirus antigen ELISA on samples.

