9.1.1 Variables and derivations

Primary endpoint:

A serum IgA response in the *neonatal* schedule, is defined as $a \ge 3$ -fold increase from baseline, where baseline is defined as stated in sections 7.1.2 and 8.1.3 for handling of missing baseline IgA measurements of this analysis plan.

Secondary endpoints:

- A serum IgA response in the *infant* schedule, is defined as a ≥ 3-fold increase from baseline, where baseline is defined as stated in sections 7.1.2 and 8.1.3 for handling of missing baseline IgA measurements of this analysis plan.
- Cumulative vaccine take is defined as vaccine take observed at the current assessment time point or following any previous dose, where vaccine take is

defined as \geq 3-fold increase in serum anti-rotavirus IgA from baseline to post IP dosing, or detectable RV3 shedding in stools (by ELISA or PCR) any day from day 3 to 5 following administration of IP.

- Shedding of RV3-BB is defined as presence of RV3-BB shedding in stool from days 3-5 following each dose of IP.
- Geometric mean titre of the anti-rotavirus serum IgA response after 3 doses of RV3-BB.
- Safety and tolerability (as per sections 15 to 16 of this analysis plan) of RV3-BB.
- Occurrence of diarrhoea episodes in participants, according to severity and detection of wild-type rotavirus.

Derivations:

A participant will, at each vaccine titre, be defined a "responder" if he/she has a serum *IgA response* (\geq 3-fold increase in serum anti-rotavirus IgA from baseline) for neonatal arms IP dose 1 - 3 and infant arm IP dose 2 - 4 of RV3-BB. The response rate will be dichotomised (0 = non-responder, 1 = responder).

Geometric means (and associated summary statistics) will be determined as follows:

- 1. Log-transform the titre data (if not already log-transformed)
- 2. Determine the arithmetic mean and other descriptive statistics of the transformed data using the PROC MEANS procedure
- Exponentiate the output obtained from the PROC MEANS procedure, depending on data to be presented (log-transfer vs not log-transformed)
- 9.1.2 Analysis

Non-inferiority of lower titre vaccines (primary as well as secondary endpoints):

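### The only by-arm rotavirus count planned for diarrhoea (SAP 9.1.10) is not limited to wild-type virus, although the objective and endpoint are, and nothing excludes excreted vaccine virus from it

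*SAP*

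**What the plan says.** The objective is the same in both documents. Protocol 4.2 has "To describe the occurrence of diarrhea episodes in participants, according to severity and detection of wild-type rotavirus", and SAP 2.1.2 repeats it. SAP 9.1.1 carries the same restriction into the secondary endpoint: diarrhoea episodes "in participants, according to severity and detection of wild-type rotavirus".

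The analysis is in SAP 9.1.10 and has two parts. The tabulated part reads "The presence of rotavirus and the severity of episodes in diarrhoea samples will be summarised (n, %) and listed by treatment group". The part that mentions wild-type virus is a listing: episodes "according to severity and strain of wild-type rotavirus will be listed".

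For routine post-dose stools, SAP 9.1.8 does separate the two kinds of virus. Only vaccine-like positives count as shedding, and "Positive PCR samples that are sequenced as 'wild type-like' by sequence analysis will not be included in RV3-BB shedding but will be listed". SAP 9.1.10 has no matching rule.

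Two assays are named for diarrhoea samples. The methodology part of the protocol synopsis says "Stool and diarrhoea samples will be tested at the local study laboratory for excretion of rotavirus using PCR". SAP 3.1.1 says "Episodes will be confirmed by Rotavirus antigen ELISA on samples", and the endpoint part of the same synopsis agrees with the SAP.

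**The concern.** A by-arm count of rotavirus in diarrhoea stools measures wild-type disease only if the virus found is wild-type. Here every participant receives three doses of a live rotavirus. A loose-stool episode with another cause, occurring while the infant is excreting vaccine virus, could be counted as rotavirus diarrhoea.

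This table is the trial's only planned by-arm summary of rotavirus in diarrhoea. If vaccine virus is included, it no longer describes the stated endpoint. A difference between arms could then reflect how much vaccine virus was excreted, not how much disease occurred.

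**Working it through.** The plan states no rate, event count or power for this endpoint, so there is no figure to reproduce. The check is a comparison of texts, followed by an illustration on assumed values.

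**Step 1: objective against table.**

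| Place | Virus specified | Form |
|---|---|---|
| Protocol 4.2, SAP 2.1.2 | wild-type | objective |
| SAP 9.1.1 | wild-type | secondary endpoint |
| SAP 9.1.10, first sentence | rotavirus, unrestricted | n (%) by arm |
| SAP 9.1.10, second sentence | wild-type strain | listing only |

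No by-arm count of the endpoint as defined is planned.

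**Step 2: can vaccine virus enter the count?**
- Protocol 3.8.1 reports excretion in the majority of infants after one dose in Phase I (the cohort aged 6-8 weeks).
- Protocol 10.1 names diarrhoea or loose motions as possible side effects.
- SAP 3.1.1 observes episodes from randomisation to 28 days after the last dose of investigational product, which covers the period after every RV3-BB dose.
- Neither the PCR nor the antigen ELISA is described as excluding vaccine strain. SAP 9.1.8 relies on sequence analysis for that.

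So vaccine virus can enter, and no stated rule removes it.

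**Step 3: can the mix differ by arm?** Under Protocol 10.5 the three neonatal arms have live virus at doses 1, 2 and 3, and the infant arm at doses 2, 3 and 4. Let *s* be the probability of shedding in the week after a live dose and *r* the diarrhoea rate per child-week. If the two are independent, with one shedding week per dose and N = 172 per arm:

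expected vaccine-positive episodes = N × *s* × (sum of *r* over the three live-dose weeks).

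*Neonatal against infant schedule.* If shedding is equal at doses 2 and 3, those terms cancel. With the same *s* at doses 1 and 4, the difference (infant minus neonatal) is

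172 × *s* × (*r* at week 14 − *r* in the first week).

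All values below are assumptions, because the documents give none:
- Equal rates at both ages: 0.
- 0.5 and 2 per 100 child-weeks (first week, week 14): 172 × 0.3 × 0.015 = 0.8, to 172 × 0.9 × 0.015 = 2.3 episodes.
- 0.5 and 4 per 100 child-weeks: 172 × 0.3 × 0.035 = 1.8, to 172 × 0.9 × 0.035 = 5.4 episodes.

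Swapping the two rates reverses the sign.

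*Among the neonatal arms.* Dose timing is identical, so it contributes nothing. A difference arises only if shedding depends on titre. At an assumed 2 per 100 child-weeks, *s* = 0.9 gives 172 × 0.02 × 3 × 0.9 = 9.3 episodes, and *s* = 0.6 gives 172 × 0.02 × 3 × 0.6 = 6.2, with no difference in disease.

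**Step 4: is a wild-type table feasible?** Protocol 8.4 and 8.6 already plan both presence and strain of rotavirus in diarrhoea samples, so the classifying data are due to be collected.

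**The case against.** The strongest reply is that the SAP is silent on vaccine virus and never says that it will be counted. SAP 9.1.1 defines the endpoint as wild-type, the objective is only to describe, and a reader could recover wild-type cases from the listing. SAP 20.1.13 also refers to a separate templates document that sets table content, and its rows may already be right. This stands as far as it goes. It makes the defect a missing restriction rather than a stated error, but the SAP text should not depend on a template to make its table match its endpoint.

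A reader might also infer a stronger point: that dose timing biases the table, with a spurious excess of rotavirus diarrhoea in newborns because the infant arm has placebo at dose 1. The documents do not support that. The dose 1 window is mirrored by dose 4, when the infant arm has live vaccine and the neonatal arms have placebo. Every arm has three live doses inside the window, and SAP 9.1.10 summarises by treatment group over the whole window. The net effect could be zero or fall in either direction. Among the three neonatal arms, timing cannot matter at all.

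Nor should a reader conclude that PCR will certainly turn excreted vaccine virus into a positive episode. The SAP endpoint names antigen ELISA, and which assay governs is unresolved.

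**Conclusion.** The mismatch holds on the text: the planned by-arm count does not measure the stated secondary endpoint and does not exclude vaccine virus. Contamination is plausible because the vaccine is live, is excreted and is given within the observation window.

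Whether it differs by arm depends on shedding by titre and on diarrhoea and shedding rates in the dose 1 and dose 4 windows. None of these is given, so size and direction cannot be stated. The episode counts in the illustration show only how the effect would arise. The endpoint is descriptive, with no test or margin, and the primary non-inferiority conclusion on serum IgA is unaffected. The change is worth making because it is cheap and the table otherwise invites misreading.

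**What to change.** In SAP 9.1.10, tabulate diarrhoea episodes by arm and by severity (modified Vesikari below 11, and 11 or above, as in Protocol Appendix 1) in four rows:

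- wild type-like rotavirus;
- RV3 vaccine-like rotavirus;
- rotavirus-positive but untypable;
- rotavirus-negative.

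Apply the sequence rule of SAP 9.1.8 to diarrhoea samples, and state that the wild-type row answers the objective. The untypable row is needed because partly untypable strains occurred in the Phase IIb trial (Protocol 3.8.3).

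State which assay defines rotavirus positivity for this endpoint, and reconcile the PCR and antigen ELISA statements.

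The cost is a few table rows and a sentence or two of SAP text. No new data are needed, because strain determination on diarrhoea samples is already planned. Protocol 8.6 lists strain testing of diarrhoea samples and sequence analysis for shedding under different laboratories, so the SAP should also say which result assigns an episode to its row.

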4.3 Exploratory Objectives

The basis of the exploratory objectives is to further understand potential barriers to rotavirus vaccine efficacy in the region. The exploratory objectives are;

- To describe Histo-blood Group Antigens (Lewis and secretor) status of participants in association with anti-rotavirus sero-conversion and cumulative vaccine take after 3 doses RV3-BB administered in either the neonatal schedule (any titre) or infant schedule.
- To assess maternal anti-rotavirus IgA and IgG levels in association with anti-rotavirus IgA seroconversion and cumulative vaccine take in participants following receipt of RV3-BB administered in either the neonatal schedule (at any vaccine titre) or infant schedule at a vaccine titre of 1 x 10⁷.
- To describe the gut microbiome in participants receiving RV3-BB administered in the neonatal schedule (at any vaccine titre) or infant schedule at a vaccine titre of 1×10^7 .
- To describe innate and adaptive immune responses in infants vaccinated with RV3-BB administered in a neonatal vaccine schedule (any titre) or in the infant schedule at a vaccine titre of 1×10^7 .

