2.1.3 Exploratory objectives

The basis of the exploratory objectives is to further understand potential barriers to rotavirus vaccine efficacy in the region. The exploratory objectives of this study are:

- To describe Histo-blood Group Antigens (Lewis and Secretor) status of participants in association with anti-rotavirus sero-conversion and cumulative vaccine take after 3 doses RV3-BB administered in either the neonatal schedule (any titre) or infant schedule.
- To assess maternal anti-rotavirus IgA and IgG levels in association with antirotavirus IgA seroconversion and cumulative vaccine take in participants following receipt of RV3-BB administered in either the neonatal schedule (at any vaccine titre) or infant schedule at a vaccine titre of 1x10⁷.
- To describe the gut microbiome in participants receiving RV3-BB administered in the neonatal schedule (at any vaccine titre) or infant schedule at a vaccine titre of 1x10⁷.
- To describe innate and adaptive immune responses in infants vaccinated with RV3-BB administered in the neonatal vaccine schedule (any titre) or in the infant schedule at a vaccine titre of 1x10⁷.

3. Endpoints

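### SAP 9.1.12 states an association objective for maternal IgA and IgG but specifies no analysis linking maternal titre to infant response

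*SAP*

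**What the plan says.** The objective is one of association. SAP 2.1.3, following Protocol 4.3, reads: "To assess maternal anti-rotavirus IgA and IgG levels in association with antirotavirus IgA seroconversion and cumulative vaccine take in participants", for infants on the neonatal schedule at any titre or on the infant schedule. SAP 9.1.12 repeats the objective as the lead-in to its maternal-antibody item and then sets out three outputs:

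- "Maternal Serum IgA and IgG titres will be summarised, by treatment group using geometric means titres", together with the log-scale mean and SD;
- a frequency table of how many values, and what share, fall under the assay's detection limit;
- a listing of individual maternal titres by arm on the FAS.

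The same section treats the histo-blood group (HBGA) objective, which is also worded as an association, differently: "Vaccine take and components of, shedding and IgA seroconversion will be summarised by HBGA phenotype", for the neonatal schedule (any titre) and the infant schedule after three doses.

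SAP section 5 moves two exploratory objectives to separate, later analysis plans: the gut microbiome, and innate and adaptive immunity. The maternal-antibody objective is not among them.

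**The concern.** The outputs planned for maternal antibody do not address the question they are listed under. None of them puts maternal titre and infant response in the same table or model.

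The question matters to the trial's rationale. Protocol 3.3 lists maternal and breast milk antibodies among the suspected reasons for low rotavirus vaccine efficacy in high-burden countries. Protocol 3.6.1 argues that neonatal strains replicate well in spite of them. Protocol 4.3 makes understanding such barriers the basis of the exploratory objectives. Maternal blood is collected and assayed for this purpose.

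If the SAP text is followed as written, the report would show maternal titres by arm and nothing on whether they relate to response. Any later analysis would have its cut-points, model and population chosen after the data are known.

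**Working it through.** The plan gives no figure to reproduce here. The check has three parts.

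**1. Is the link made anywhere else in the SAP?**

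| Place | What it contains | Maternal titre linked to response? |
|---|---|---|
| Section 5 | Defers microbiome and immune-response objectives | No; this objective is not deferred |
| 7.1.3 | Possible subgroups: gender, delivery route, race/ethnicity | No |
| 9.1.2 | GEE on dose, vaccine group and their interaction | No |
| 9.1.12, HBGA | Take, shedding and seroconversion by phenotype | No (exposure is phenotype) |
| 9.1.12, maternal | Titre summaries, below-detection counts, listings | No |
| 11.1.2 | Logistic model for exclusion from the PP set | No; the outcome is PP exclusion and maternal titre is not a covariate |

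**2. Can by-arm summaries show the association?** SAP 3.1.3 places the maternal sample before the study or at Visit 1, so the infant's allocation cannot affect it. Under randomisation its expected distribution is the same in every arm, whatever its relation to response.

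A simulation illustrates this. Assumptions: log maternal titre standard normal, four arms of 120, average response 50%, 2,000 simulated trials.

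| True odds ratio per SD | Mean log titre in each arm | SD of an arm mean | Responder minus non-responder mean |
|---|---|---|---|
| 1.0 (no association) | about 0.00 | 0.091 | 0.00 |
| 0.5 (strong association) | about 0.00 | 0.091 | -0.62 SD |

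The SD agrees with theory: 1/√120 = 0.091. The planned summary is the same in both rows. The contrast that does change is not planned.

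**3. What could the data show for IgA response?** Inputs from SAP 8.1.1: 172 infants per arm, 30% excluded from the PP set, 50% response assumed for the active controls. Applying that 50% to every arm is an assumption.

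- Evaluable per arm: 172 × 0.70 = 120.4, about 120.
- Pooled neonatal schedule: 3 × 120 = 360. Infant schedule: 120.
- Approximate detectable odds ratio per SD of log titre: exp[(z₀.₉₇₅ + z_power) / √(n·p·(1−p))]. For 90% power the numerator is 1.96 + 1.2816 = 3.2416.
- n = 360, p = 0.50: √90 = 9.487; 3.2416/9.487 = 0.342; odds ratio about **1.41**.
- n = 120, p = 0.50: √30 = 5.477; 3.2416/5.477 = 0.592; odds ratio about **1.81**.

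These do not carry over to cumulative take. The only guide in the documents is the Phase IIb trial (Protocol 3.8.3): 78/83 (94%) on the neonatal schedule and 83/84 (99%) on the infant schedule.

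- n = 360, p = 0.94: √(360 × 0.94 × 0.06) = √20.3 = 4.506; 3.2416/4.506 = 0.719; odds ratio about 2.05.
- Expected non-takers, neonatal: 360 × 5/83 ≈ 22.
- Expected non-takers, infant: 120 × 1/84 ≈ 1.4. A model of take would be barely estimable there.

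Take in Malawi may differ. At rates near these, a model of take is weak or unworkable.

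**The case against.** Several points on the other side have force.

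- **The item is exploratory.** Primary, secondary and safety conclusions do not depend on it. This stands, and it limits the weight of the point. It does not explain why HBGA gets a linking summary and maternal antibody does not.
- **The SAP does more than tabulate means by arm.** It also plans below-detection counts and participant-level listings. That is correct, but neither is an analysis of association.
- **The output templates may contain the missing table.** SAP 20.1.13 refers to a separate templates document that is not available here. The point is therefore limited to the SAP text, which specifies no such analysis for a template to display.
- **Regression goes beyond the SAP's own standard.** HBGA gets only a descriptive summary, so parity requires only a cross-tabulation. This is fair: the descriptive summary is the core of the fix and the model is an addition, for IgA response only.

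A reader might infer that the trial cannot answer the question or that the data are lost. The documents do not support that. Maternal and infant titres are both collected and listed (SAP 9.1.3 and 9.1.12), so the association can still be examined, though not as a pre-specified analysis.

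A reader might also pool all four arms (4 × 120 = 480) and claim a smaller detectable odds ratio. The objective is framed by schedule. IgA baselines also differ between schedules, being cord blood on the neonatal and pre-second-dose serum on the infant (SAP 7.1.2). A figure for 480 would match no sensible planned model.

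**Conclusion.** The point holds for the SAP text: the objective is carried into 9.1.12, but the analyses given there cannot address it, and no other section supplies or defers the analysis. It is worth correcting because the remedy is cheap and the question is part of the trial's rationale. It does not bear on the non-inferiority conclusion.

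For IgA response, about 1.41 per SD (n = 360) and 1.81 per SD (n = 120) are approximate detectable odds ratios at 90% power. They rest on 50% response in every arm, 30% PP exclusion and a maternal sample for every infant. Two features make them optimistic:

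- Protocol 6.2 keeps a baby in the trial when maternal blood cannot be collected, so n may be smaller.
- Protocol 10.6 puts multiple births in the same arm, and such siblings share one maternal titre, so they are not independent. The documents do not give their expected number, so this loss cannot be sized.

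It would be tempting to apply the same figures to cumulative take. The Phase IIb take rates do not support that.

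**What to change.** Add to SAP 9.1.12, separately for the pooled neonatal schedule and the infant schedule:

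1. **Descriptive summary, in parallel with HBGA.** Number and proportion with IgA seroconversion and with cumulative vaccine take after three RV3-BB doses, by category of maternal IgA and of maternal IgG (for example quartiles). Also maternal geometric mean titre by responder status.
2. **Model for IgA response only.** Logistic regression on log maternal IgA and, separately, on log maternal IgG. Adjust for arm in the pooled neonatal model, cluster standard errors by mother, and report odds ratios with 95% confidence intervals.
3. **Cumulative take.** Keep it descriptive if non-takers are few.
4. **Reporting.** Name the analysis set, give the number of infants with a maternal sample, and label the results exploratory. Limit any power statement to IgA response, with the assumptions above.

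The existing by-arm summaries can stay as a check of balance.

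The cost is a few lines of SAP text and a few extra exploratory tables. Two antibodies by two schedules gives four models. With two outcomes, the categorical summaries number 2 × 2 × 2 = 8. These are several comparisons without multiplicity adjustment, which the report should say. No new samples or assays are needed, and the primary analysis is unchanged.
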